Medication compliance will be facilitated and increased by several complementary methods. First, participants will receive automated reminders sent daily to their cell phone. These messages will remind them to take their study medication and can be sent via SMS text-message. These prompts also remind participants to contact study staff if they have any side effects or barriers to compliance. This strategy has been successfully implemented in previous addiction trials^{12,132,133}. Medication bottles will also be equipped with a medication event monitoring system (smart caps). Smart caps are reusable and provide a time stamped medication use/bottle access. They also provide a programmable visual and auditory reminder of administration time to increase compliance. At all medical monitoring and study visits medication compliance will be assessed by study staff via pill count and download of smart caps logs.

C6. NPU Stress-Reactivity Task

Participants view a series of colored square "cues" on a computer in a blocked design^{19,22}. There are three block types: No Shock (N), Predictable Shock (P), and Unpredictable Shock (U). Each type of shock block is presented twice and the no shock blocks are presented three times, with blocks counterbalanced both within- and between-subjects (e.g., 2 block orders: PNUNUNP, UNPNPNU). All blocks include 6 cues presented for 5s in the center of the computer monitor separated by a

variable inter-trial-interval (ITI; mean 15s, range 10-20s). Electric shock is administered .25s prior to cue offset during every cue in the Predictable shock blocks so that the appearance of the cue 'predicts' that the shock will occur in a few seconds. Electric shock is administered at pseudo-random times during both cues and ITIs in the Unpredictable shock blocks so that the occurrence of the shock is completely unpredictable by the participant. Six electric shocks are administered in each Predictable and Unpredictable shock block. No electric shock occurs during the no-shock blocks. Participants are verbally informed of the cue-shock contingencies to ensure robust block differences. The task lasts approximately 20min.

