The primary dependent measure in the NPU task is startle potentiation. The eye-blink startle response is elicited with a binaurally presented acoustic startle probe (50ms, 102dB white noise with near instantaneous rise time). Startle probes occur at 4.5s post cue-onset on a random subset of 4 cues in every block. Serial position of startle probes across the three block types (No Shock, Predictable Shock, Unpredictable Shock) is counterbalanced within-subjects. Electromyogram (EMG) activity to the startle probes is recorded from two Ag-AgCl sensors placed according to published guidelines beneath the eye over the orbicularis oculi muscle¹³⁴. Electromyogram activity is sampled at 2000Hz with an online bandpass filter (1-500Hz) using NeuroScan Grael bioamplifiers (Compumedics USA, El Paso, TX). Offline processing includes a high-pass filter (4th order 28Hz Butterworth filter), creating epochs from 50ms pre-probe to 250ms post-probe, signal rectification and smoothing (30Hz lowpass filter). The startle response is quantified as the peak amplitude 20-100ms post-acoustic probe onset relative to a 50ms pre-probe baseline. Startle potentiation during cues is calculated separately for unpredictable and predictable blocks as the difference between response to probes during shock and no-shock blocks. After the NPU task, participants retrospectively report their negative affective state during each block type (Post-Experimental Questionnaire, PEQ). We recently found this self-report measurement is sensitive to the anxiolytic effects of alcohol^{79,80}.

C7. Brief Motivational Interventions

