AIM 1: Unpredictable startle potentiation from the NPU task at 4 weeks will be analyzed in separate general linear models controlling for baseline NPU responses (Visit 1) with repeated measures on Condition (unpredictable vs. predictable shock). A between-subjects regressor for Treatment (8 mg doxazosin vs. placebo) will be included. Aim 1 predictions will be supported by significant Treatment X Condition interactions with doxazosin producing selectively larger reduction in startle potentiation during unpredictable relative to predictable shock.

AIM 2: Any heavy drinking (coded yes vs. no dependent if the participant reported any days where they consumed >4 drinks per day in men/ >3 drinks per day in women during the medication period) will be analyzed in a generalized linear models with a between-subjects regressor for Treatment (8 mg doxazosin vs. placebo). To be conservative, this analysis will be pursued as an intent to treat (ITT) analysis. Aim 2 predictions will be supported by significant Treatment effects with doxazosin producing selectively lower proportion of participants reporting any heavy drinking. This outcome is measured at Visits 2 & 3 and can be obtained even if the participant arrives with positive BAC.

Timeline

This project will be completed within five years of its funding. This goal is reasonable given our team's expertise in conducting both randomized controlled trials and psychophysiological laboratory research working with drug administration, community participants, and stress reactivity. Based on prior recent experience with a similar population of alcoholics who completed multiple laboratory visits, we anticipate that 85% of participants who complete the first visit will return to complete the study. We can complete up to five study visits per week and expect to average approximately 3 study visits per week to account conservatively for no-shows, failed eligibility criteria, equipment failure, and other data loss. We anticipate completing data collection in 4 years, allowing time at the beginning of the grant period for set-up and final pilot testing and the end of the grant period for manuscript preparation.

Protection of Human Subjects

D1. Risks to the Subjects

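### NPU block order is counterbalanced but not named in the Aim 1 model, so any non-linear habituation adds avoidable noise to the Treatment x Condition contrast

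*Combined protocol and SAP*

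**What the plan says.** Section C6 (NPU Stress-Reactivity Task) describes seven blocks: "Each type of shock block is presented twice and the no shock blocks are presented three times". They are presented "with blocks counterbalanced both within- and between-subjects", and the illustration is "e.g., 2 block orders: PNUNUNP, UNPNPNU".

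On the startle probes, C6 says: "Startle probes occur at 4.5s post cue-onset on a random subset of 4 cues in every block". It adds: "Serial position of startle probes across the three block types (No Shock, Predictable Shock, Unpredictable Shock) is counterbalanced within-subjects". The outcome is scored as follows: "Startle potentiation during cues is calculated separately for unpredictable and predictable blocks as the difference between response to probes during shock and no-shock blocks".

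Under Statistical Analysis, the Aim 1 model is described as "controlling for baseline NPU responses (Visit 1) with repeated measures on Condition (unpredictable vs. predictable shock"). For treatment: "A between-subjects regressor for Treatment (8 mg doxazosin vs. placebo) will be included". Aim 1 is decided on the Treatment x Condition interaction. The opening paragraph of that section puts days abstinent at Visit 1 into every model and lists individual-difference moderators for secondary analyses. Block order is in neither place. C3 names sex as the only randomization stratum. No section says whether a participant keeps the same block order at Visits 1 and 2.

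**The concern.** The Treatment x Condition interaction is the arm difference in U minus P. Both potentiation scores subtract the same no-shock response, so that term drops out of U minus P and cannot absorb an effect of block position. In one example order the P blocks are first and last and the U blocks lie inside them; in the other order this is reversed. If startle falls quickly early in the task and then levels off, the outer pair averages higher than the inner pair, and U minus P moves down in one order and up in the other.

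The design creates this factor on purpose. A model without it leaves the resulting spread in the error term of the deciding contrast. The baseline covariate is the same contrast measured at Visit 1, so it carries its own order shift. That shift helps the adjustment if the order is repeated and harms it if the order changes. What is at stake is the precision of the Aim 1 estimate.

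**Working it through.** **Inputs from the documents.** Two example orders; 2 P, 2 U and 3 N blocks; potentiation scored as shock minus no-shock; Aim 1 model with Treatment, Condition, baseline NPU response and days abstinent; 80 per arm; 85% of those completing the first visit expected to complete the study, so 0.85 x 80 = 68 per arm. The documents give no alpha, power, effect size, SD or habituation curve, so there is no planned figure to reproduce.

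**Step 1: block positions.**

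| Order | P | U | N | Mean position (P, U, N) | Mean squared position (P, U) |
|---|---|---|---|---|---|
| PNUNUNP | 1, 7 | 3, 5 | 2, 4, 6 | 4, 4, 4 | 25, 17 |
| UNPNPNU | 3, 5 | 1, 7 | 2, 4, 6 | 4, 4, 4 | 17, 25 |

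Equal mean positions make the linear contribution to U minus P exactly zero within each participant. Unequal mean squares show that curvature remains, with opposite sign in the two orders.

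**Step 2: size of the shift under assumed curves.** Let A(k) be the response in block k, with the same time course for all block types. The shift is mean(A3, A5) minus mean(A1, A7) in the first order and its negative in the second.

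- Exponential decline towards zero, total drop 50% by block 7: mean(0.794, 0.630) - mean(1, 0.5) = 0.712 - 0.750 = -0.038 of the first-block response. A 30% drop gives 0.012 and a 70% drop 0.091 in absolute value.
- Decline towards an asymptote, half-life 2 blocks, as a share of the total drop: mean(0.429, 0.143) - mean(1, 0) = 0.286 - 0.500 = -0.214. Half-lives of 3 and 1 blocks give 15% and 36%.
- Limit, with all habituation after block 1: 50% of the drop.

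**Step 3: cost without baseline adjustment.** Write the shift as +/-c, in units of the within-order SD of U minus P, with the orders split 50:50. Ignoring order multiplies the variance by 1 + c². Take two-sided alpha 0.05 and 80% power with order modelled (d = 0.48 at 68 per arm), all assumed. Power with order ignored is 79.6% at c = 0.1, 78.4% at 0.2 and 76.5% at 0.3. The equivalent loss, 68 x (1 - 1/(1 + c²)), is 0.7, 2.6 and 5.6 participants per arm.

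**Step 4: cost with the planned baseline adjustment.** Let rho be the within-order correlation of U minus P between visits, and v = 1 + c². With order modelled, residual variance is 1 - rho². With order ignored it is:

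- same order at both visits: v - (rho + c²)²/v
- order drawn independently at each visit: v - rho²/v
- order switched between visits: v - (rho - c²)²/v

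Example, c = 0.4 and rho = 0.7, so v = 1.16 and 1 - rho² = 0.51:

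- same: (1.16 - 0.86²/1.16)/0.51 = 0.522/0.51 = 1.024
- independent: (1.16 - 0.49/1.16)/0.51 = 0.738/0.51 = 1.446
- switched: (1.16 - 0.54²/1.16)/0.51 = 0.909/0.51 = 1.782

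Excess residual variance, range over rho = 0.3 to 0.7 (assumed):

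| c (assumed) | Same order | Independent | Switched |
|---|---|---|---|
| 0.1 | 0.2% to 0.5% | 1.2% to 2.9% | 1.8% to 5.6% |
| 0.2 | 0.7% to 2.1% | 4.8% to 11.5% | 7.1% to 21.8% |
| 0.3 | 1.5% to 4.4% | 10.7% to 25.6% | 15.3% to 46.8% |
| 0.4 | 2.4% to 7.4% | 18.9% to 44.6% | 25.6% to 78.2% |

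**Step 5: type I error.** A simulation with no treatment effect, c = 0.3, the two orders split equally and at random over 136 participants, and order ignored rejected in 4.4% of 4,000 runs. The Monte Carlo standard error at 5% is sqrt(0.05 x 0.95/4000) = 0.34 percentage points, so there is no sign of inflation.

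**The case against.** The case for leaving the plan alone is substantial.

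- **The design already removes most of the problem.** Both orders are palindromes, so linear habituation is gone before any modelling, and probe position is also counterbalanced within subjects. This stands. It does not remove the contrast between blocks 1 and 7 and blocks 3 and 5, which is where curvature enters.
- **The orders are only an example, and the analysis section says that it describes models briefly.** This stands in part. The analyst may intend to include order. But these are the only orders given, and with blocks counterbalanced between subjects an order factor exists whatever the final list. A term that is not written down is not pre-specified.
- **Steep decline at block 1 is not established.** C6 implies 4 x 7 = 28 cue probes in a task of about 20 minutes, whereas section D2 allows up to 75 noise bursts over about 30 minutes. If some bursts come before block 1, the steepest habituation may be over by then. The documents do not settle this, so a small effect is quite possible.
- **The planned baseline adjustment absorbs much of the shift.** This is true if the order is repeated at Visit 2, where the excess is at most 7.4% over the range shown. It fails if the order changes.

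A reader might go further and infer that all habituation is left in the contrast, or that chance imbalance of order between arms biases the treatment estimate. Neither follows. The linear part cancels exactly. Chance imbalance is part of the sampling variance already counted in the standard error, not a second harm.

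**Conclusion.** The point holds as a minor matter of precision. Order is a factor built into the design, it is not named in the Aim 1 model, and the non-linear part of any habituation reaches the deciding contrast with opposite sign in the two orders. If order is independent of arm, Treatment x Condition remains unbiased and type I error is not inflated.

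The size cannot be fixed from the documents. The ranges depend on an assumed shift of 0.1 to 0.4 within-order SD, an assumed visit-to-visit correlation of 0.3 to 0.7, an equal split of the two example orders and equal variance at both visits. Under these, the excess runs from negligible (0.2% to 7.4%) with a repeated order to possibly material with independent (1.2% to 45%) or switched (1.8% to 78%) orders. A reader might take the upper figures as the expected loss. The documents do not support that, because they say neither that order changes between visits nor that habituation is steep enough to give a shift of 0.4 SD.

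**What to change.** Add block order at Visit 2, crossed with Condition, to the Aim 1 model; equivalently, use order as a covariate for U minus P. State in C6 whether a participant keeps the same order at Visits 1 and 2. If order is always kept or always switched, Visit 2 order determines Visit 1 order and one term is enough. If it is drawn afresh at each visit, add Visit 1 order too, so that the baseline covariate is also cleared of its shift. It would help to state that order is assigned independently of treatment arm.

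The cost is wording plus one or two degrees of freedom, with no new data provided the order used at each visit is recorded. If the order effect is small, the gain is little or none.

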Recently abstinent (1-8 weeks) alcoholics will be recruited to participate in an eight-week double-blind, randomized placebo-controlled trial (RCT) examining the effects of an α 1-NE antagonist (doxazosin) on the defensive (physiological) response to stressors using a well-validated animal-human translational stressor task (NPU task). Study Visit 1 provides a pre-treatment baseline assessment of participants' NPU task stress-sensitivity prior to doxazosin/placebo administration. Next, participants are randomly assigned between-subjects to initiate an 8-week dose escalation schedule up to 8 mg maximum doxazosin dose or placebo as they continue their efforts to abstain from alcohol. After four weeks (Study Visit 2) of treatment, participants will return to complete the NPU task again, and at both four weeks (Study Visit 2) and eight weeks (Study Visit 3), to assess clinical outcomes. These visits allow for evaluation of the effect of a therapeutic dose of doxazosin on the early surrogate endpoint of stress-reactivity (unpredictable shock threat in NPU task; Visit 2; **AIM 1**) and proximal clinical outcomes (heavy drinking days; Visits 2 & 3; **AIM 2**).

C2. Participants and Recruitment Sites

Participants: We will recruit abstinent alcoholics (38% female) aged 18-65 years. Participants will meet criteria for Alcohol Use Disorder with at least moderate severity (>4 DSM-5 criteria) and be at least one but no more than eight weeks abstinent from alcohol use at Screening Visit, and still abstinent at Visit 1. Participants who are eligible at screening but lapsed at Visit 1 will be rescheduled when they are again at least 1 week abstinent. Participants will be excluded if they have a lifetime history of severe and persistent mental illness (SPMI; e.g., bipolar disorder, schizophrenia, suicidal ideation or psychosis) or current substance use disorder and is not currently pursuing abstinence (other than alcohol or nicotine). Participants with co-morbid Axis 1 disorders will be included unless they are using medications that affect the startle response or contraindicate doxazosin use.

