Study staff will then prepare the participant for the NPU task with the application of physiological sensors. Next participants receive a series of shocks of increasing intensity (7 mA maximum) to assess their subjective tolerance threshold as per standard procedures from our laboratory^{22,128}. Their subjective maximum tolerated shock from the screening visit is used during the NPU tasks at both Visit 1 and Visit 2 to minimize individual differences in subjective pain tolerance. Next participants complete the NPU task (see below). After the NPU task, participants will be randomly assigned to drug group (doxazosin vs. placebo; between-subjects) in a stratified blocked schedule by sex using urn randomization procedures^{129,130}. The randomization and double-blind will be implemented and maintained by the UW Pharmaceutical Research Center (see letter of support), which is located in the same building as the CRU. All participants are told that they will receive either doxazosin or placebo during the study, but neither the participants nor the research staff will be aware of the group they are randomized to receive. Participants who are off study and were consented under a previous protocol which promised unblinding will still be unblinded, via phone contact after their last visit.

Participants will take the first study medication dose at home that evening after Study Visit 1 (Treatment Day 1). Staff will call participants on Day 2 to confirm initial compliance and monitor any adverse events. Participants continue 8 weeks of treatment including an 18-day escalating dose schedule up to a therapeutic dose (8 mg) of doxazosin (or placebo; see Doxazosin Dosing Schedule below). Additionally, participants will attend four medical monitoring visits during the first month of treatment (see below).

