If the participant affirms that they drove themselves, we will offer to call a cab or a friend to drive them. If this offer is declined, we will suggest that they should stay in the CRU or ARC until their BAC registers below 0.03. This release criterion has been used for many years in our other UW research that involves alcohol administration to research participants. As such, it seems equally appropriate for release for an ineligible participant who has self-administered their own alcohol. By way of comparison, a BAC of 0.08 is considered per se evidence of impairment from alcohol and with a BAC of > 0.05 alcohol impairment can be considered a contributing factor when accident or injury occurs.

If the participant declines to stay and indicates they plan to drive themselves, we will tell the participant that we will call the campus police so that the participant can make a more informed decision about what course of action to take. If the participant continues to indicate they plan to drive, we will call the campus police if the participant is driving away and provide information about the possibility of an impaired driver in the vicinity. We will not reveal the participant's name to the police in order to protect their confidentiality.

Statistical Analysis:

Planned Data Analysis for Specific Aims

Analyses for quantitative and dichotomous dependent measures will be accomplished within either General or Generalized (binomial family with logit link function) Linear Models, respectively, using R¹⁴⁰. In the sections below, we briefly describe the primary factors in statistical models to evaluate each Specific Aim. All models will include number of days abstinent at Visit 1 as an interactive between-subjects regressor to evaluate if drug effects and outcomes are comparable across alcoholics who vary in their previous duration of abstinence (1-8 weeks) on study initiation, although this has not moderated the effects on NPU task in our preliminary studies. Numerous individual difference measures (e.g., sex, mood/anxiety disorder comorbidity, tobacco use, trait affect, alcohol dependence severity, other treatment) are available to add to these models as interactive between-subject regressors in secondary analyses to evaluate possible individual difference moderators of drug effects.

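### Sex stratifies the randomisation but is in neither primary model; add it, and in the same edit state at what value of days abstinent Treatment is read

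*Combined protocol and SAP*

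**What the plan says.** C3. General Procedures assigns participants to arm "in a stratified blocked schedule by sex using urn randomization procedures". Sex is the only stratification factor named.

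Planned Data Analysis for Specific Aims specifies the models:

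- **Aim 1:** a linear model with Treatment, "controlling for baseline NPU responses (Visit 1) with repeated measures on Condition (unpredictable vs. predictable shock"). Success is a significant Treatment × Condition interaction.
- **Aim 2:** a logistic model for any heavy drinking with a Treatment regressor, and "Aim 2 predictions will be supported by significant Treatment effects". The endpoint threshold differs by sex: "consumed >4 drinks per day in men/ >3 drinks per day in women during the medication period".
- **Both aims:** "All models will include number of days abstinent at Visit 1 as an interactive between-subjects regressor". No centring, reference value or type of test is given.

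Sex is named once among possible covariates, in the sentence that opens "Numerous individual difference measures (e.g., sex, mood/anxiety disorder comorbidity". That sentence says these measures "are available to add to these models as interactive between-subject regressors in secondary analyses".

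C2. Participants and Recruitment Sites requires one to eight weeks of abstinence at screening. Anyone eligible who has "lapsed at Visit 1 will be rescheduled when they are again at least 1 week abstinent".

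**The concern.** Stratifying makes the arms alike in their sex mix. If the analysis then ignores sex, any sex difference in outcome stays in the error term although it no longer contributes to chance differences between arms. The standard error is then too large for the design and the Treatment test rejects too rarely. The sex-specific drinking threshold does not itself show that sex is prognostic, but it confirms that sex must be recorded for every participant.

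The days-abstinent term raises a separate question of reading. Once Treatment interacts with days, the Treatment coefficient describes the effect at one value of days. With raw days that value is 0, outside the eligible range. What is at stake is power; with no effect and no interaction there is no false-positive risk.

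**Working it through.** **Inputs from the documents.** 80 per arm (C4); 38% female (C2), so 0.38 × 80 = 30.4, taken as 30 women per arm; 85% expected to complete (Timeline), so 0.85 × 80 = 68 per arm for Aim 1; logit link for Aim 2.

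**Assumptions.** The documents give no event rates, sex effect or distribution of days, and no power calculation to reproduce. I took two-sided 5% tests, varied event rates and sex effects, and used days uniform on 7 to 56 with no true interaction.

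**Sex, Aim 2.** Logistic model with Treatment × centred days, with and without sex, Wald test. There were 10,000 simulated trials per power scenario and 20,000 per null. Overall event rates were held fixed as the sex effect varied. Gains are paired, with error of about 0.1 point. Power gain in points from adding sex:

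| Event rates | Sex log-odds 0 | 0.4 | 0.8 |
|---|---|---|---|
| 50% vs 30% | 0.2 | 0.7 | 1.5 (74.1% to 75.6%) |
| 40% vs 20% | 0.2 | 0.4 | 1.0 |
| 60% vs 40% | 0.1 | 0.4 | 1.3 |

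At sex log-odds 0.8, type I error is 4.5 to 4.6% without sex and 4.9 to 5.1% with it.

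**Sex, Aim 1.** The Treatment × Condition test compares arms on the unpredictable-minus-predictable difference, so a plain sex main effect cancels. A mixed-model check gave the same interaction estimate (−0.25631) and SE (0.25248) with and without it. Only sex × Condition can help. The simulations used 40,000 power and 60,000 null trials at 68 per arm, adjusted for baseline and Treatment × centred days, with the effect set for about 80% power after adjusting for sex:

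| Residual variance of the difference explained by sex | Power without / with sex | Type I error without / with sex |
|---|---|---|
| 2% | 79.1 / 79.5% | 4.8 / 4.9% |
| 5% | 78.4 / 80.0% | 4.5 / 5.0% |
| 10% | 76.6 / 79.8% | 4.2 / 5.0% |

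If sex explains nothing, adding it costs 0.1 point (79.7% vs 79.6%).

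A formula check agrees. For a standardised sex difference d, R² = 0.38 × 0.62 × d² / (1 + 0.38 × 0.62 × d²). Unadjusted type I error is 2[1 − Φ(1.96/√(1 − R²))]. At d = 0.5, R² = 0.0589/1.0589 = 0.056 and type I error is 4.4%.

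**Days abstinent.** In a Treatment × days model, the variance of the Treatment effect read at x, relative to reading it at the mean, is 1 + ((x − mean)/SD)². For uniform 7 to 56 the mean is 31.5 and the variance is 49²/12 = 200.1. At x = 0 the SE ratio is √(1 + 31.5²/200.1) = 2.44. A test with 80% power at the mean then has Φ(2.80/2.44 − 1.96), about 21%. Visit 1 follows screening, so days can exceed 56: 7–63 gives 2.38, 14–63 gives √(1 + 38.5²/200.1) = 2.90, and 14–70 gives 2.78.

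Simulated Aim 2 power by type of Treatment test (sequential means Treatment entered first):

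| Event rates | Raw-days coefficient | Centred coefficient | Sequential | Type II |
|---|---|---|---|---|
| 50% vs 30% | 17.7% | 73.5% | 73.6% | 73.8% |
| 40% vs 20% | 18.5% | 79.6% | 80.5% | 80.3% |
| 60% vs 40% | 17.3% | 71.3% | 71.1% | 71.4% |

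With no effect and no interaction, type I error is 4.7 to 5.1% for the raw coefficient and 5.1% for the centred one. In Aim 1, crossing raw days with Treatment × Condition gave 20.9% power when sex explains nothing.

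**The case against.** The strongest reply is that the sex item is close to negligible on its own figures. There is no bias and no inflated type I error, and every gain rests on a sex effect that the documents do not supply. In Aim 1, sex must predict the difference between conditions after adjustment for baseline, which may absorb much of any stable sex difference. The simulated conservatism also assumes exact balance by sex. The plan describes both blocked and urn allocation, and urn balance is only approximate, so the true type I error would lie nearer 5%. The analysis section also calls its account brief, so the absence of sex is partly an inference.

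On days abstinent, the large loss needs raw days, a retained interaction, and a coefficient or Type III test. The natural sense of a Treatment effect is an overall one.

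Most of this stands as a limit on size. It does not remove the point: placing sex among optional secondary moderators is hard to square with its being a primary covariate, and adding it has almost no cost even if sex does nothing. The text does not exclude the harmful reading of days. The plan also leaves open whether days cross with Treatment × Condition in Aim 1, although making days interactive in all models to check drug effects points that way.

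**Conclusion.** The point holds. The randomisation is stratified by sex and neither primary model includes it. The omission invalidates neither test. The gain from adding sex is small: up to 1.5 points of power in Aim 2 at a sex log-odds of 0.8, and up to 3.2 points in Aim 1 if sex explains 10% of the residual variance. The loss if sex has no effect is at most about 0.1 point.

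The days-abstinent clarification involves a much larger number, roughly 71–80% power falling to 17–19% in Aim 2. That is a risk under one reading of the text, and sequential and Type II tests escape it.

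Confidence is high on what the documents say and on the direction of the effects. The sizes depend on assumed event rates, sex effects and distribution of days.

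**What to change.** Amend the SAP wording as follows:

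- **Aim 2:** add sex as a main effect.
- **Aim 1:** add sex and sex × Condition.
- **Days abstinent:** keep the planned interaction. Mean-centre days, preferably at the mean of all randomised participants, or use a marginal Treatment contrast. State that Treatment (Aim 2) and Treatment × Condition (Aim 1, if days cross with it) are read at mean days abstinent.
- **Moderation:** keep Treatment × sex as a secondary test.

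No new data are needed and no planned analysis is removed or demoted. The cost is one degree of freedom in Aim 2 and two in Aim 1. The Aim 2 log-odds ratio becomes conditional on sex as well as days. At sex log-odds 0.8 and 50% vs 30%, its size moves from 0.87 to 0.91 and its SE from 0.338 to 0.347, so the ratio of estimate to SE rises from 0.87/0.338 = 2.57 to 0.91/0.347 = 2.62. Because the Aim 2 prediction is worded in terms of proportions, a standardised difference in proportions is worth reporting beside the odds ratio.
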